The Role of Skin Care Regimen in Skin Health

NCT03497130

April 5, 2018

Date: 04/05/2018

Principal Investigator: [name], MD

Application Number: IRB00165140

JHM IRB - eForm A – Protocol

The Role of Skin Care Regimen in Skin Health

1. Abstract

Dry skin is not a disease entity but it is an important patient matter as it can significantly decrease a person's quality of life. Individuals with dry skin experience discomfort associated with itching, skin tightness, and irritation. The lack of proper hydration is one of the most apparent characteristics of dry skin, which is associated with erythema and scaling on the skin surface. Skin care products with moisturizing features have beneficial effects in the treatment of dry skin. The aim of our study is to evaluate the role of a regular skin care regimen comprising of a mild cleanser and moisturizer in improving dry skin and overall skin health.

This study will have a study population of up to 100 individuals over the age of 18. Each study participant will have up to 3 on-site visits within 4 weeks. Select participants will be asked to apply a mild cleanser and moisturizer daily for 2 weeks. To assess the effects of a regular skin care regimen, clinical evaluations, digital photography, and subject questionnaires will be obtained during the study.

2. Objectives

- The primary aim of the study is to evaluate the role of a regular skin care regimen comprising of a mild cleanser and moisturizer in improving dry skin and overall skin health.
- The secondary aim of the study is to assess quality of life improvement with a routine skin care regimen.

3. Background

Dry skin is a common phenomenon and can dramatically decrease a person's quality of life as well as contribute to a wide variety of skin diseases. Individuals with dry skin experience discomfort associated with itching, skin tightness, and irritation¹. The lack of proper hydration is one of the most apparent characteristics of dry skin, which is associated with erythema and scaling.² Dry skin is caused by the interaction of lifestyle and environmental factors. Hereditary factors and advanced age can also contribute to dry skin. The severity of dry skin is usually exacerbated by the frequent use of harsh cleansers, the lack of moisturization, and by cold, dry air^{3,4}.

Skin care products are topical preparations with mainly moisturizing feature which have beneficial effects on dry skin. Skin care products hydrate the skin and breaks the dry skin cycle⁵. There are many mild cleansers and moisturizers widely available for improvement of dry skin. However, many healthcare providers and patients overlook the importance of skin care products and a regular skin care regimen. Numerous studies show that usage of mild cleansers and moisturizers hydrates and improves dry skin and appearance.⁶⁻¹³. While there is extensive evidence of benefits of using mild cleansers and moisturizers, much of the previous studies are limited to the effects of

Date: 04/05/2018

Principal Investigator: [name], MD

Application Number: IRB00165140

single cleanser or moisturizer. Skin care regimens incorporating regular use of a mild cleanser and moisturizer have not been assessed.¹⁴⁻¹⁶. This study aims to evaluate the role of a regular skin care regimen comprising of a mild cleanser and moisturizer in improving dry skin, skin appearance, and overall skin health.

4. Study Procedures

a. Study design, including the sequence and timing of study procedures

Recruitment: Individuals will be recruited from patient populations seen at the general dermatology clinics of Johns Hopkins Department of Dermatology or from patient populations participating in Johns Hopkins Cutaneous Translational Research Program (CTReP) research studies. Interested study participants will be evaluated after their routine clinical care visits. Participants will also be recruited from other patient populations at the Johns Hopkins Hospital through the use of flyers and online advertisements. Study procedures will be conducted at the Johns Hopkins CTReP office located at the Johns Hopkins Outpatient Center. Recruitment may include Johns Hopkins University employees or students, but these groups will not be specifically targeted for participation. Interested individuals will be interviewed to ascertain whether they meet the basic eligibility criteria to participate in the study. Once eligibility has been demonstrated, the potential subjects will be directed to make their first study appointment. We will recruit up to 100 participants over the age of 18 with dry, itchy skin and they will be split into 2 groups. Participants will be randomly assigned to skin care regimen group (approximately 75% of total enrolled) and control group (approximately 25% of total enrolled). All evaluation will be conducted similarly in both groups.

Visit 1

During the first scheduled appointment, the research protocol will be discussed with the subject, and documentation will be obtained of the subject's consent to participate in the study as well as the subject's agreement to be contacted about future research studies.

Once informed consent is obtained, individuals will undergo a washout period of one week in which they are asked to refrain from the use of all moisturizers on their skin. Participants will be supplied with a skin cleanser, Dove[®] Soap, to use during this period and application log. All applications should be reported in the application log by the participants.

During this visit, investigators will also perform clinical assessment, take photographs and administer subject questionnaires.

Visit 2 (Baseline):

Date: 04/05/2018

Principal Investigator: [name], MD

Application Number: IRB00165140

All participants will return after the washout period. Participants in the skin care regimen group will receive Vaseline[®] Moisturizer, Dove[®] Soap, and application log. These participants will be asked to apply the Vaseline[®] Moisturizer twice a day and use Dove[®] Soap daily for 2 weeks. All applications should be reported in the application log by the participants. A demonstration and verbal instructions for how and where to apply the products will be provided to the subjects along with the application log for daily use. Individuals not in the skin care regimen group will continue with the provided Dove[®] Soap.

During this visit, investigators will perform clinical assessments, take photographs and administer subject questionnaires.

Visit 3 (day 14±2):

During this visit, investigators will perform clinical assessment, take photographs and administer subject questionnaires. Application logs will be returned.

Clinical assessment: Clinical assessments will be performed 1) to record baseline skin findings, 2) to evaluate skin status by visual scoring, and 3) to identify any occurrence of any adverse events.

Photography: Standardized digital photographs will be obtained by study staff using a digital camera and software under standard photographic conditions. Photograph files will be coded to remove personal identifiers and stored on a secure hard drive in CTReP.

- b. Study duration and number of study visits required of research participants.
The study consists of up to 3 on-site visits within 4 weeks. We will allow 1 year to complete the study.
- c. Blinding, including justification for blinding or not blinding the trial, if applicable.
NOT APPLICABLE
- d. Justification of why participants will not receive routine care or will have current therapy stopped.
NOT APPLICABLE
- e. Justification for inclusion of a placebo or non-treatment group.
NOT APPLICABLE
- f. Definition of treatment failure or participant removal criteria.

Any clinical findings determined by the Investigator to be important and/or unusual will be referred to as an adverse event (AE). Study participants will be asked to contact clinic staff immediately if they experience an adverse reaction to the products at any time during the study.

Date: 04/05/2018

Principal Investigator: [name], MD

Application Number: IRB00165140

Such reactions may be documented in a problem events log. The Investigator will use her discretion to remove participants from the study, and all problem events will be reported to IRB.

- g. Description of what happens to participants receiving therapy when study ends or if a participant's participation in the study ends prematurely.
NOT APPLICABLE

5. Inclusion/Exclusion Criteria

Inclusion:

1. Participants must be over the age of 18 years old with dry, itchy skin;
2. Participant must be willing to comply with the requirements of the protocol;
3. Participant must have the ability to understand and communicate with the investigator;
4. Participant must provide informed consent.

Exclusion:

1. Subjects who are unable to provide informed consent;
2. Subjects who are unable to refrain from swimming or hot tub use or no more than 2 showers per day throughout the study duration
3. Subject with significant medical history or current skin diseases that the investigator feels is not safe for study participation;
4. Subjects who have been treated with systemic retinoids or steroids within the past month prior to entry to the study;
5. Subjects who have been treated with topical steroids, retinoids or other topical drugs within 2 weeks prior to entry to the study;
6. Recently treated or current skin diseases that would affect clinical evaluation;
7. Subjects who self-report that they are pregnant or nursing;
8. Patients with history of investigational drug use in the 30 days prior to entry into the study.

6. Drugs/ Substances/ Devices

- a. The rationale for choosing the drug and dose or for choosing the device to be used.

NOT APPLICABLE

- b. Justification and safety information if FDA approved drugs will be administered for non-FDA approved indications or if doses or routes of administration or participant populations are changed.

NOT APPLICABLE

Date: 04/05/2018

Principal Investigator: [name], MD

Application Number: IRB00165140

- c. Justification and safety information if non-FDA approved drugs without an IND will be administered

NOT APPLICABLE

7. Study Statistics

- a. Primary outcome variable.
Clinical/visual scores and subjective score from subject questionnaires.
- b. Secondary outcome variables.
Adverse effects reported by participants and investigator.
- c. Statistical plan including sample size justification and interim data analysis.
Analysis will include paired and unpaired t-tests with two-tailed p-values. Values obtained at baseline, in middle of the study and after completing the study will be compared. The difference of measure values will be compared between application group and control group.
- d. Early stopping rules.
If the participant wishes to withdraw from the study for any reason, or if the primary caretaker or study investigators wish to cease use of the products.

8. Risks

The moisturizing lotion and wash are generally very well tolerated. Rarely, they can induce a burning sensation, dryness, skin irritation, erythema, stinging, sensitization, and dermatitis. Possible side effects from the product applications include irritant and allergic reactions. Irritation from these agents can be improved or relieved when participants stop using the products. Risk events, problems, and deviations will be reported by the PI directly to the IRB.

In terms of confidentiality, there are minimal risks as all study participant information will be de-identified. No confidential or protected information would be taken beyond the standard. There is a slight financial risk to the participants in the rare event that the above complications occur, requiring additional medical care.

9. Benefits

Date: 04/05/2018

Principal Investigator: [name], MD

Application Number: IRB00165140

Patients with dry skin in the skin care regimen group may experience improvement in their overall skin health. There will be no direct benefit to the participants in the control group. In addition, there is also the potential benefit to society at large. We hope to assess the role of a routine skin care regimen in improving dry skin and reducing symptoms. This can improve quality of life for patients who suffer from dry skin.

10. Payment and Remuneration

Study participants who undergo all study procedures, including correct application of moisturizing lotion and wash in the skin care regimen group will receive a total of \$60 at completion of the study.

11. Costs

Study costs will be covered by the UniLever Corp.

12. References

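### The protocol names cold, dry air as worsening dry skin and allows a year to complete, but neither the allocation nor the t-tests account for calendar time; the cost is precision and chance seasonal imbalance, not bias

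*Combined protocol and SAP*

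**What the plan says.** - **Prognostic factor.** Section 3 (Background) says the severity of dry skin is "usually exacerbated by the frequent use of harsh cleansers, the lack of moisturization, and by cold, dry air".
- **Time frame.** Section 4b: "The study consists of up to 3 on-site visits within 4 weeks", and "We will allow 1 year to complete the study". Section 4a sets a one-week washout and then two weeks to Visit 3, so each person contributes about 3 weeks.
- **Allocation.** Section 4a (Recruitment): "We will recruit up to 100 participants over the age of 18 with dry, itchy skin and they will be split into 2 groups", then "Participants will be randomly assigned to skin care regimen group (approximately 75% of total enrolled) and control group (approximately 25% of total enrolled". No sequence generation, blocking, stratification or concealment is described, and nothing links allocation to date of entry. Section 4c marks blinding as not applicable.
- **Analysis.** Section 7c: "Analysis will include paired and unpaired t-tests with two-tailed p-values", and "The difference of measure values will be compared between application group and control group". No baseline, season or date term is named. No alpha, effect size, standard deviation or sample size calculation is given.

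**The concern.** The protocol itself identifies weather as something that changes the condition being scored. Follow-up is short relative to the permitted study period, so one participant may be measured in January and another in July. Season can affect how dry the skin is at Visit 2, and possibly how the score moves over the following two weeks.

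The paired comparisons within the regimen group cannot separate weather from product, so the between-group comparison has to do that. It does so on average over randomizations. In any one trial, however, about 25 controls can by chance be spread over the year differently from the other 75. Part of the observed difference in that trial then reflects season, and nothing in the design or analysis reduces it. Even with good balance, seasonal variation that is not modelled stays in the error term.

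**Working it through.** The documents give no figure to reproduce, so the size is worked out under stated assumptions.

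**Inputs.** From section 4a: N = 100 (a ceiling), split 75 and 25. Assumed: half enrol in cold months; two-sided alpha of 0.05; season effects as given below.

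**1. Chance imbalance at 3:1.** With a fixed 75/25 split, the number of cold-month controls is hypergeometric (100 people, 50 cold, 25 drawn).
- SD of the gap in cold-month share = √[0.5 × 0.5 × (1/25 + 1/75) × 100/99] = √0.01347 = 0.116, or 11.6 points.
- Exact probabilities: gap of at least 10 points, 0.356; at least 15 points, 0.165; at least 20 points, 0.063.
- A gap of 20 points or more needs 8 or fewer, or 17 or more, cold-month controls. For example, 17/25 = 68% against 33/75 = 44% is a gap of 24 points.

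**2. Sensitivity.** With only 25 of 100 enrolled in cold months, the three probabilities are 0.293, 0.111 and 0.062. If only 40 people enrol (30 and 10, half cold), a gap of at least 20 points has probability 0.273.

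**3. Role of the ratio.** At 1:1 the SD is √[0.25 × (1/50 + 1/50) × 100/99] = 0.1005. The ratio 0.116/0.1005 is about 1.15, so 3:1 adds about 15%.

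**4. Effect on the test.** With season effects of 0, 0.5 and 1 SD on the analysed outcome, the simulated type I error of the unadjusted t-test without blocking is 0.048 to 0.050. Among trials where the gap happens to be 20 points or more, it is about 0.075 (0.5 SD) and 0.15 (1 SD).

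**5. Precision.** With half in cold months, a season effect of g SD explains 0.25g²/(1 + 0.25g²) of the variance: 5.9% at g = 0.5 and 20% at g = 1. Removing a share R² multiplies the standard error by √(1 − R²): √0.95 = 0.975 and √0.80 = 0.894. Simulated blocking gives reductions of about 3% to 10% over the same range.

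**6. Blocking.** With 3:1 permuted blocks in order of entry, the SD of the gap falls from 11.6 points to 2.7 (blocks of 4) or 3.5 (blocks of 8). No simulated trial had a gap of 15 points or more. The plain t-test then becomes conservative: with blocks of 4, type I error is 0.044 at 0.5 SD and 0.031 at 1 SD. The analysis therefore needs a matching term.

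**7. Which calendar term.** Assume dryness follows a yearly sine curve and entry is even over the year.
- A cold/warm split explains 8/π² = 81% of the seasonal level.
- For change over 14 days it explains 0.81 × sin²(2π × 7/365) = about 1%, because worsening and improving weeks fall in the same half-year.
- Four quarters explain [sin(π/4)/(π/4)]² = 81% of either.
- The largest 14-day change is sin(14π/365) = 12% of the yearly peak-to-trough range.

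**The case against.** The strongest reply is that randomization already deals with this. Imbalance in season is ordinary sampling error, of the same kind as imbalance in age, and the t-test's standard error allows for it. That is correct, and step 4 confirms it.

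A reader might infer that season is confounded with group, that the false-positive rate is inflated, or that the 3:1 ratio causes the problem. The documents support none of these. Section 4a states random assignment, overall type I error is preserved, and the ratio adds little. Nor do the documents say that allocation is unrestricted: a blocked list fits the approximate percentages equally well. The plan simply does not say.

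Four further points reduce the size:
- No section says that scores drift over two weeks, and on the sine curve such drift is small.
- If the compared differences are changes from Visit 2 to Visit 3, a constant seasonal level cancels. Section 7c does not say so clearly, and season-dependent change would remain.
- Everyone enters with dry, itchy skin and has the same washout, which probably narrows seasonal differences at baseline.
- Once the right season term is in the model, blocking adds little: with a season effect explaining 20% of the variance, the adjusted standard error is 0.207 without blocks and 0.206 with blocks of 4.

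What remains is that the protocol names a prognostic factor, leaves it unhandled in both design and analysis, and could handle it cheaply. Blocking still protects where the modelled shape of season is wrong, and specifying it would also supply the missing description of sequence generation and concealment.

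**Conclusion.** The point holds as a modest, inexpensive improvement in precision and balance. At the maximum enrolment, with half in cold months, the seasonal gap between arms has an SD of 11.6 points and reaches 20 points in about 6% of trials; smaller enrolment makes large gaps more likely. The gain from handling season is about 3% to 10% in standard error if it explains 5% to 20% of the variance, and less otherwise.

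The cold-month share, the season effect and the alpha level are all assumptions, because the documents give none of them. One year is an allowance, so enrolment within a single season would largely remove the issue. Bias would arise only if allocation in practice shifted over calendar time. Nothing in the documents indicates that, although no described procedure excludes it.

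**What to change.** **Section 4a.** Replace the allocation sentence with wording such as: *Participants are assigned 3:1 (regimen to control) from a concealed computer-generated list in permuted blocks of varying size (multiples of 4), used in order of entry.*

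**Section 7c.** Replace the unpaired t-test with a linear model, for each primary score, of the Visit 3 value on group, Visit 2 value and calendar time of Visit 2. Use season or quarter, or randomization block, rather than only a cold/warm split. Record the date of Visit 2.

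**Cost.** Two text changes and no extra participants, visits or staff. Quarter uses 3 degrees of freedom; block uses more (24 if 100 people are in 25 blocks of 4), so quarter is the lighter choice. Block sizes must be varied and kept from those enrolling participants: the trial is not described as blinded, and in a known block of 4 every assignment after the single control can be predicted.

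### No rule governs moisturizer use before the Visit 3 visual scoring, so the between-group difference can mix an immediate on-skin effect with improvement between applications

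*Combined protocol and SAP*

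**What the plan says.** All places are in the combined protocol and SAP.

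- **Before baseline (section 4a, Visit 1).** Everyone goes one week without any moisturizer, using the supplied soap. The Visit 2 score is therefore planned to be free of moisturizer in both arms.
- **After baseline (section 4a, Visit 2).** For the regimen arm: "These participants will be asked to apply the Vaseline[®] Moisturizer twice a day and use Dove[®] Soap daily for 2 weeks". For controls: "Individuals not in the skin care regimen group will continue with the provided Dove[®] Soap".
- **Endpoint visit (section 4a).** The heading "Visit 3 (day 14±2" gives the window. The visit consists of clinical assessment, photographs and questionnaires, and the logs are handed back. One purpose of the clinical assessment is "to evaluate skin status by visual scoring".
- **Allocation (section 4a, Recruitment).** Participants are randomized to "skin care regimen group (approximately 75% of total enrolled) and control group (approximately 25% of total enrolled").
- **Outcome and analysis (sections 7a and 7c).** The primary outcome consists of clinical or visual scores and a questionnaire score. Changes are compared between the groups with two-tailed t-tests.

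No section says when moisturizer was last to be applied before the Visit 3 scoring.

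**The concern.** The plan controls product on the skin before the first of the two scores that it compares, and not before the second. At Visit 3 the regimen arm is in the middle of twice-daily use. Someone who moisturizes that morning and attends an hour later is fully compliant, and so is someone who leaves the morning application until after the visit. If fresh product changes how skin looks, the score reflects that as well as any change in the skin between applications. Controls are given nothing that could produce the same effect.

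Randomization does not help, because the effect arises at measurement and follows from the allocated treatment. Later analysis does not help either unless the time since application was recorded. What is at stake is interpretation: a better visual score in the regimen arm could mean skin that looks better just after moisturizing, skin that is better between applications, or both. The plan does not say which is meant.

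The point concerns the visual score and, as supporting material, the photographs. It does not concern the questionnaires.

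**Working it through.** **1. Does any text close the gap?** Four places come near it.

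- The instructions at Visit 2: "verbal instructions for how and where to apply the products will be provided to the subjects along with the application log for daily use". These cover method and site, not timing relative to the visit.
- The photographic standard: "using a digital camera and software under standard photographic conditions". This fixes the equipment and setting, not the state of the skin.
- The log: "All applications should be reported in the application log by the participants". Applications are recorded. Clock times are not mentioned, and no analysis or visit rule uses the log.
- The statement under Recruitment that both groups are evaluated alike. This governs how assessors work. It cannot equalize the skin when only one arm is given moisturizer.

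None of them sets or records the time since application.

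**2. How many participants?** At the maximum of 100: 0.75 × 100 = 75 regimen and 0.25 × 100 = 25 control.

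**3. Size of the shift.** Let p be the share of the regimen arm scored with an immediate effect d on the visual score. The mean change in that arm moves by p × d, and so does the between-group difference. If a share q of controls used a moisturizer of their own with the same effect, the shift would be (p − q) × d. The documents give none of p, q or d, so the shift cannot be calculated.

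**4. Could a modest effect matter at this sample size?** This is an illustration on assumptions that are not in the documents: SD of change 1, two-sided alpha 0.05, 75 versus 25, q = 0, no improvement between applications, normal approximation. The regimen-arm SD is √(1 + p(1 − p)d²), and the standard error is √(that SD² / 75 + 1/25).

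- d = 0.5, p = 1: SE = √(1/75 + 1/25) = 0.231; 0.5 / 0.231 = 2.17; probability of a significant result 0.58.
- d = 0.5, p = 0.5: shift 0.25; SD = √1.0625 = 1.031; SE = 0.233; probability 0.19.
- d = 0.25: probability 0.19 for p = 1 and 0.08 for p = 0.5.

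These figures treat the whole immediate effect as unwanted, which is itself an assumption. They show sensitivity, not expected bias.

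**5. What would a visit-day hold do to the interval?** Assume applications at 08:00 and 20:00, and visits from 09:00 to 17:00.

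- Applied that morning: 08:00 to 09:00 is 1 h, and to 17:00 is 9 h (8 h wide).
- Morning application left until after the visit: 20:00 to 09:00 is 13 h, and to 17:00 is 21 h (8 h wide).
- A mixture, as the plan now allows: 1 to 21 h (20 h wide).
- With the hold, evening application at 20:00: 13 to 21 h. With evening application anywhere from 18:00 to 24:00: 24:00 to 09:00 is 9 h, and 18:00 to 17:00 next day is 23 h (14 h wide).

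The hold reliably removes same-day product. It narrows the interval compared with a mixture, but not compared with everyone having applied that morning.

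**The case against.** The strongest reply is that the immediate effect is the treatment. Section 3 names skin appearance among the aims, the comparison is a regimen against soap alone, and the plan nowhere claims a benefit that lasts without product. Scoring people while they use the regimen as instructed answers a legitimate question. This stands to the extent that the effect cannot simply be called bias. It does not remove the point, because the plan does not say that this is its target, and the time since application would still be uncontrolled.

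It is also fair that no passage says recent application changes this score, by how much or for how long, and that staff could give such an instruction verbally. The first limits what can be claimed. The second is not in the plan, and section 10 ties payment to applying the products correctly, which may encourage an application on the visit morning.

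A reader might infer more than the documents support:

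- **That no control has moisturizer on the skin at Visit 3.** The ban is written for the washout week and is not repeated for controls after Visit 2. What can be said is that they are given no study moisturizer.
- **That regimen participants seen late are scored after stopping.** Two weeks of use and a window to day 16 could suggest a gap of up to 16 − 14 = 2 days. The return of the logs at Visit 3 fits use up to the visit better, so nothing here relies on that gap.
- **That the photographs are a primary outcome.** Section 7a does not list them, and no section says that they are scored.

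**Conclusion.** The concern holds in a limited form. The plan leaves study-moisturizer use before the Visit 3 visual scoring open, after a moisturizer-free baseline. The between-group difference in the visual part of the primary outcome can therefore combine an immediate on-skin effect with improvement between applications. The gap applies to the whole regimen arm, about 75 of up to 100.

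It would be tempting to conclude that a positive visual result would be spurious. The documents do not support that: they give no size for the immediate effect, and part of it may be wanted. The supported conclusion is that a reader could not tell which state of the skin had been measured and, unless clock times happen to be logged, that analysts could not separate the two afterwards. This rests on the reading that use continues up to the visit, and on the possibility, not shown in the documents, that fresh product affects the score. It deserves correction because the remedy is cheap and the loss cannot be repaired later.

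**What to change.** Add to the Visit 2 and Visit 3 text in section 4a:

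- In the regimen arm, moisturizer use continues through the evening before the actual Visit 3.
- On the visit day, no moisturizer goes on the skin to be assessed until scoring and photographs are done. Both arms receive this instruction.
- The clock time of the last application is entered in the existing log.

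Add to section 10 that observing the hold counts as applying the products correctly for payment.

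The cost is a short addition to the visit instructions, one log entry, one payment clause and one delayed application, with no extra visit or procedure. The observed effect may be somewhat smaller. The hold leaves any residual effect from the previous evening and does not fix the interval exactly. If the sponsor prefers to measure skin with product in use, the plan should say so and still record the time of the last application.

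### Section 4c treats blinding as not applicable, yet an investigator's visual score is part of the primary outcome and nothing keeps the scorer from knowing the arm

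*Combined protocol and SAP*

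**What the plan says.** Section 4c requests "Blinding, including justification for blinding or not blinding the trial, if applicable". The answer is NOT APPLICABLE, with no reason. Section 4a (Recruitment) describes random assignment, about 75% to the regimen and 25% to control, of up to 100 participants. It adds: "All evaluation will be conducted similarly in both groups".

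Under Visit 2 (Baseline) the regimen group receives moisturizer, soap and a log. For the others: "Individuals not in the skin care regimen group will continue with the provided" soap. The same visit includes "A demonstration and verbal instructions for how and where to apply the products will be provided to the subjects" and also the baseline assessment: "During this visit, investigators will perform clinical assessments, take photographs and administer subject questionnaires". No order of tasks is given. At Visit 3 the assessment is repeated and the logs are handed back.

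The clinical assessment includes visual scoring of skin status. Section 7a makes the clinical/visual scores and the questionnaire score the primary outcome. Section 7c plans paired and unpaired two-tailed t-tests, with the differences compared between groups.

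Standardized photographs are taken at all three visits. Their file coding removes personal identifiers; arm and visit are not mentioned, and section 7 gives the photographs no role.

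**The concern.** Blinding of the assessor is a live question in any randomized comparison whose outcome is a judgement by eye. The form asks for a justification even when a trial is not blinded, and here none is given.

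No text names a masked or independent scorer, separates dispensing from scoring, states when randomization happens, or asks participants to keep their arm from the scorer. Scoring and dispensing share Visit 2; scoring and log return share Visit 3. Using the same evaluation procedure in both groups is good practice, but it is not masking.

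Participants cannot be masked, because one arm gets a moisturizer and the other does not. The questionnaire component is therefore open to expectation bias in any case. That leaves the visual score as the only primary component that could be protected, and as written it is not. If scorers, knowing the arm, rate the regimen group somewhat better at Visit 3, the result cannot be told apart from a moisturizer effect.

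**Working it through.** **Inputs.** From the documents: up to 100 participants, about 75% and 25% (section 4a); unpaired two-tailed t-test on the difference (section 7c). Not in the documents, so assumed: a 95% interval (two-sided alpha 0.05), SD of the analysed change set to 1, and the size of any bias. There is no planned figure to reproduce, because section 7c gives no effect size, SD, alpha or power.

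**How bias enters.** Let b2 and b3 be the mean scoring bias at Visits 2 and 3, for regimen (R) and control (C). The expected between-group difference in change is

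true difference + β, where β = (b3R − b2R) − (b3C − b2C).

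A bias that is equal at both visits cancels. A bias that appears only once the arm is known passes in full. β does not involve the sample size.

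**Standard error, in SD units,** is √(1/n1 + 1/n2):
- 75 versus 25: √(1/75 + 1/25) = 0.231. With t(0.975; 98 df) = 1.984, the 95% half-width is 0.458.
- 45 versus 15 (60 enrolled, since 100 is a maximum): √(1/45 + 1/15) = 0.298. With t(0.975; 58 df) = 2.002, the half-width is 0.597.

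**Coverage of a 95% interval** is P(−t ≤ T ≤ t), with T noncentral t and noncentrality β/SE:

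| Assumed β (SD) | β/SE at 75 v 25 | Coverage 75 v 25 | Coverage 45 v 15 |
|---|---|---|---|
| 0 | 0 | 0.950 | 0.950 |
| 0.10 | 0.43 | 0.929 | 0.937 |
| 0.25 | 1.08 | 0.812 | 0.869 |
| 0.50 | 2.17 | 0.427 | 0.622 |

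Coverage does not depend on whether the moisturizer works. A simulation of 40,000 runs at 75 versus 25 gave 0.929 / 0.809 / 0.427 for these three biases with no true effect, and 0.930 / 0.812 / 0.424 with a true effect of 0.5 SD. If there is no true effect, one minus coverage is the false-positive rate: 7.1%, 18.8% and 57.3% at 75 versus 25.

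**Masked reading with partial failure.** Suppose a share u of images is unmasked and the residual bias is u × β (proportionality is an assumption). At 75 versus 25:

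| Assumed β (SD) | u = 25%: residual β, coverage | u = 50%: residual β, coverage |
|---|---|---|
| 0.10 | 0.025, 0.949 | 0.050, 0.945 |
| 0.25 | 0.0625, 0.942 | 0.125, 0.917 |
| 0.50 | 0.125, 0.917 | 0.250, 0.812 |

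**What photographs might lose.** At 75 versus 25, power for an assumed true difference of 0.65 SD is 0.796. If photographs capture 90% or 80% of it (0.585 or 0.52 SD), power is 0.708 or 0.606. If the photographic score also has a 10% larger SD, power is 0.626 or 0.527. At 45 versus 15 (equal SD) the figures are 0.573 for the full difference and 0.488 or 0.404 for the reduced ones.

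**Reading time.** Visits 2 and 3: 100 × 2 = 200 sets; at 2 to 5 minutes, 200 × 2/60 = 6.7 h to 200 × 5/60 = 16.7 h. All three visits: 300 sets, 10 to 25 h.

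**The case against.** The strongest reply is that this is a short study of over-the-counter products in which participants cannot be masked, that an open-label design is defensible, and that photographic scoring is not plainly better than scoring in person. Much of this stands. Photographs miss tactile signs, the plan names no visual scale or body sites, and a twice-daily moisturizer may leave visible residue. On the assumptions above, power falls from 80% to 61–71%, or lower. These are good reasons not to make a photographic score the main result or to demote the live score. They do not excuse an empty answer in 4c or the unordered tasks at Visits 2 and 3.

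Stronger readings are tempting but unsupported:
- A reader might infer that scorers are told the arm, or that the visual result will be biased. The documents say neither; they only fail to prevent it.
- A reader might take the Benefits section, which expects no direct benefit for controls, as proof of the scorer's expectation. It is a statement about participants, and its effect on scoring is inference.
- A reader might say that the logs reveal the arm. At Visit 1 every participant gets one ("All applications should be reported in the application log by the participants"), and the return of logs at Visit 3 is not limited to one group. Visit 2 lists a log only for the regimen group, so a log could give a clue, no more.
- A reader might add section 4e, also answered NOT APPLICABLE. That concerns the justification of the control group and is a separate matter.

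**Conclusion.** The point holds and should be fixed. A component of the primary outcome is judged by investigators in a randomized comparison, blinding is dismissed without a reason, and no provision masks the scorer. This is a route for bias that can be narrowed at little cost. It is not evidence that bias will occur.

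Its actual size cannot be derived. The drop in coverage to about 93%, 81% or 43% at 75 versus 25 rests on assumed net biases of 0.1, 0.25 and 0.5 SD, and the severity does not depend on those figures. Masked reading reduces the problem without removing it: at an assumed 0.5 SD bias, coverage recovers to about 92% if a quarter of images are unmasked, but only 81% if half are. The questionnaire component is unaffected. Confidence is high that the gap exists; it is lower on cost and on how much masked photographs would recover.

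**What to change.** 1. **Order the tasks.** State when randomization occurs. Both arms have the same washout, so allocation can stay undisclosed until the Visit 2 score, photographs and questionnaires are complete; only then dispense and demonstrate products. At Visit 3, complete the visual score before logs are returned or reviewed, and ask participants not to tell the scorer their arm. Where existing staffing allows, use a scorer who did not dispense.
2. **Add a masked check.** Have an existing investigator score the planned photographs in shuffled order, with participant, arm and visit labels removed, on a scale and body sites fixed in writing beforehand. Analyse this score with the same between-group comparison and report it beside the live score as a prespecified check. Keep the live score's status, and do not require both to be significant.
3. **Answer 4c.** Suggested text: Participants are open-label. Photographs are read with participant, arm and visit labels removed; visible residue may unmask some. The live clinical score and the questionnaire score remain open to bias from knowledge of the arm.

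**Cost.** Item 1 is nearly free. Item 2 adds a written scale and list of sites, relabelling of files, and about 7 to 17 hours of reading for Visits 2 and 3. Section 7c also compares a mid-study value; reading all three visits takes 10 to 25 hours. If only two are read, say that the third has no masked score. All three items need a protocol revision. The documents give no staffing, so if no existing investigator is free to read, only items 1 and 3 apply, and the sentence on photographs drops out of 4c.
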